5.5.14 Early study termination

The study can be terminated at any time for any reason by Novartis. Should this be necessary, the patient should be seen as soon as possible and treated for a prematurely withdrawn patient. The investigator may be informed of additional procedures to be followed in order to ensure that adequate consideration is given to the protection of the patient's interests. The investigator will be responsible for informing the Institutional Review Board/Independent Ethics Committee (IRBs/IECs) of the early termination of the trial.

6 Visit schedule and assessments

[Table 6-1](#) (screening epoch [Epoch 1] and the randomized treatment epoch [Epoch 2]) and [Table 6-2](#) (randomized withdrawal epoch [Epoch 3] and open-label treatment epoch [Epoch 4]) list all of the assessments and indicate with an “x” when the visits are performed.

Patients are to be seen for all visits, preferably on the designated day. The proposed visit day is displayed in [Table 6-1](#) and [Table 6-2](#).

Patients who prematurely withdraw from Epoch 2 for any reason should be scheduled for a visit when all the assessments listed for Day 113 will be performed.

Patients who prematurely withdraw from Epoch 3 for any reason should be scheduled for a visit when all the assessments listed for Day 281 will be performed.

Patients who prematurely withdraw from Epoch 4 for any reason should be scheduled for a visit when all the assessments listed for Day 785 will be performed.

If a patient refuses to return for these assessments or is unable to do so, every effort should be made to contact him/ her by telephone to determine the reason for discontinuation.

At a minimum, patients will be contacted for safety evaluations and a follow-up visit or phone call for SAEs must be performed 30 days following Investigational treatment discontinuation (TD), Premature subject withdrawal (PSW) or 8 weeks after last injection of study drug, whichever is later.

Documentation of attempts to contact the patient should be recorded in the patient record.

**Table 6-1 Assessment schedule:
Screening epoch (Epoch 1) and randomized treatment epoch (Epoch 2)**

Epoch	Screening (Epoch 1)	Randomized treatment epoch (Epoch 2)						
Visit	1	101	102	103	104	105	199 and/ or PSW	Safety follow-up
Week		1	3	5	9	13	17	
Day	-84 to -3	1	15	29	57	85	113	PSW +30 or 8 weeks after last injection¹
Informed consent	X							
Informed consent for pharmacogenetic sampling ²	X							
Participation in previous study CACZ885D2203/ MPP treatment plan CAC/885D2207M	X							
Demography	X							
Inclusion/Exclusion Criteria	X	X						
Relevant medical history/ current medical conditions	X							
Prior and concomitant medications (including vaccination status)	X	X	X	X	X	X	X	
Surgical and medical procedures	X	X	X	X	X	X	X	
Disease characteristics	X							
Determination of TB status: QuantiFERON [®] -TB Gold in Tube (QFT-GIT) assay, PPD skin test and/ or chest X-ray (as stipulated by local guidelines)	X							
Hepatitis B and C screen	X							
HIV screen	X							

Epoch	Screening (Epoch 1)	Randomized treatment epoch (Epoch 2)							Safety follow-up
		101	102	103	104	105	199 and/ or PSW		
Visit	1	101	102	103	104	105	199 and/ or PSW		
Week		1	3	5	9	13	17		
Day	-84 to -3	1	15	29	57	85	113	PSW +30 or 8 weeks after last injection ¹	
Pregnancy test – Serum* (for females of child bearing potential)	X								
Pregnancy test – Urinalysis (for females of child bearing potential)		X							
Physical examination*	S	S		S	S	S	S		
Height	X				X ³			X ³	
Weight*	X	X	X	X	X	X	X		
Blood pressure and pulse*	X	X	X	X	X	X	X		
Body temperature*	X	X	X	X	X	X	X		
ECG*	X							X	
Index flare onset		X							
PGA	X	X	X	X	X	X	X		
Physician's severity assessment of key disease-specific signs and symptoms		X	X	X	X	X	X		
Review eDiary instructions	S								
PPGA ⁴	X	X	X	X	X	X	X		
AIDAI ⁴	X	X	X	X	X	X	X		
SF-12® (to be completed by patients ≥18 years of age at Baseline)		X		X				X	
CHQ-PF50© (to be completed by patients >5 <18 years of age at Baseline)		X		X				X	

Epoch	Screening (Epoch 1)	Randomized treatment epoch (Epoch 2)							Safety follow-up
		101	102	103	104	105	199 and/ or PSW		
Visit	1	101	102	103	104	105	199 and/ or PSW		
Week		1	3	5	9	13	17		
Day	-84 to -3	1	15	29	57	85	113	PSW +30 or 8 weeks after last injection ¹	
Follow-up visit or phone call for SAEs*									X

TD = Investigational treatment discontinuation

PSW = Premature subject withdrawal

X = assessment to be recorded on clinical data base

S = assessment to be recorded on source documentation

*These assessments are also to be conducted for patients who discontinue

#These assessments are source documentation only and will not be entered into the CRF

¹ To be performed 30 days following Day 113 or PSW or 8 weeks after last injection of investigational drug, whichever is later for all patients **not** entering Epoch 3

² Only applicable for patients > 16 years of age

³ Only applicable for pediatric patients

⁴ The AIDAI and PPGA will be completed by the patient on an electronically diary daily from Screening till TD or PSW

⁵ Applicable for patients whose index flare has not resolved by Day 15. Blinded-escape add-on treatment may be initiated from Day 8 to Day 28

⁶ Applicable for patients on randomized treatment who flare on/ after Day 29 or patients on blinded-escape who will still have “mild”, “moderate” or “severe” disease activity (PGA ≥ 2 [clinical flare] and CRP ≥ 30 mg/L [serological flare]) or re-flare

Table 6-2 **Assessment schedule:**
Randomized withdrawal epoch (Epoch 3) and open-label treatment epoch (Epoch 4)

TD = Investigational treatment discontinuation

PSW = Premature subject withdrawal

X = assessment to be recorded on clinical data base

S = assessment to be recorded on source documentation

*These assessments are also to be conducted for patients who discontinue

#These assessments are source documentation only and will not be entered into the CRF

¹ To be performed 30 days following TD or PSW, or 8 weeks after last injection of investigational drug, whichever is later

² Only applicable for TRAPS patients rolling-over from CACZ885D2203/ CACZ885D2207M i.e. patients directly entering Epoch 3 following screening

³ Only applicable for pediatric patients

⁴ The AIDAI and PPGA will be completed by the patient on an electronically diary daily till Day 281 or PSW

⁵ Patients up-titrated to q4w administration in Epoch 4, will come back every 4 weeks for unscheduled visits at Day 309, Day 365, Day 421, Day 477, Day 533, Day 589, Day 645, Day 701 and Day 757 in addition to the scheduled visits

6.1 Information to be collected on screening failures

All patients who have signed informed consent but not entered into the next epoch will have the study completion page for the screening epoch, demographics, inclusion/exclusion, and serious adverse event (SAE) data collected. Adverse events that are not SAEs will be followed by the investigator and collected only in the source data.

6.2 Patient demographics/ other baseline characteristics

Patient demographic and baseline characteristic data to be collected on all patients include: date of birth, age, sex, race, ethnicity, source of patient referral, relevant medical history/ current medical condition present before signing informed consent. Where possible, diagnoses but not symptoms will be recorded.

Detailed information on the patient's vaccination status (to be recorded as part of prior medication), disease diagnosis and disease related prior medications/ surgical and medical procedures before signing informed consent will also be collected.

Investigators will have the discretion to record abnormal test findings on the medical history CRF whenever in their judgment, the test abnormality occurred prior to the informed consent signature.

All baseline characteristics to be collected are also listed in [Table 6-1](#).

6.2.1 Determination of tuberculosis status

Determination of TB status will be required before administration of study treatment ([Table 6-1](#)) and needs to be re-assessed at Day 281 and Day 785 ([Table 6-2](#)).

Selection of the most suitable test or combination of tests for detection of *M. tuberculosis* infection as listed in [Section 6.2.1.1](#), [Section 6.2.1.2](#) and [Section 6.2.1.3](#) should be made as defined by local guidelines.

Any significant findings at screening will be recorded in the “Relevant medical history/ Current medical conditions” section of the eCRF.

Any significant findings *after providing written informed consent* for participation in the study must be recorded as Adverse Events.

6.2.1.1 QuantiFERON®-TB Gold In-Tube assay

A QuantiFERON®-TB Gold In-Tube (QFT-GIT) assay may be carried out by the Central Laboratory to assess the TB status of patients.

This blood-based assay is specific for *Mycobacterium tuberculosis* and is not influenced by previous Bacillus Calmette-Guérin (BCG) vaccination or exposure to other Mycobacteria species. This test, in contrast to the Purified Protein Derivative (PPD) skin test, is also insensitive to a booster effect since the patient is not exposed to the vaccine. The assay measures the production of interferon-gamma and puts it into relation to a negative and a positive control sample. Further information is given by ([Manuel and Kumar 2008](#)).

Details about sample processing are to be described in the Central Laboratory Manual.

6.2.1.2 PPD skin test

A PPD skin test may be initiated to evaluate for an occult infection with TB if required by local regulations. The test dose is bioequivalent to 5 tuberculin units (or as according to local standard practice) of standard PPD usually injected intradermally into the volar surface of the forearm. The injection site will be cleansed and the PPD extract will then be injected into the most superficial layer under the skin. If given correctly, the injection should raise a small wheal of about 5 mm, which resolves within 10-15 minutes.

A reaction will be measured in millimeters of induration (hard swelling) after 48h – 72h. A PPD skin induration >5 mm is interpreted as positive result. This will determine whether the patients have had a significant reaction to the PPD skin test.

In case of a positive PPD skin test result and the absence of clinical signs of active tuberculosis and no history of BCG vaccination, the clinical investigator will, according to local guidance, decide whether this subject should undergo further clinical, laboratory and radiological examinations before deciding to initiate prophylactic treatment for latent TB infection. Level of TB risk is defined in [Appendix 4](#). A chest x-ray or QFT-GIT assay is however required to further investigate the nature of the positive PPD skin test as recommended by many local guidelines. In case of a negative confirmatory test, the patient is eligible for participation/ continuation in the study and no further clinical investigations are needed.

Patients with a positive PPD skin test result may be eligible for participation/ continuation only if they have a negative chest x-ray ([Section 6.2.1.3](#)) or negative QFT-GIT assay (refer to [Section 6.2.1.1](#)).

The investigator will either obtain PPD skin tests on his own and be reimbursed by Novartis for its cost or be supplied with them by the Novartis affiliate, depending on the local Novartis policy.

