4.2 Exclusion criteria

Patients fulfilling any of the following criteria are not eligible for inclusion in this study. No additional exclusions may be applied by the investigator, in order to ensure that the study population will be representative of all eligible patients.

1. Use of the following therapies:
 - a. Corticosteroids (prednisone equivalent > 0.2 mg/kg/day [or greater than the maximum of 15 mg/ day for children over 60 kg]) within 1 week prior to Baseline
 - b. Anakinra within 24 hours prior to Baseline
 - c. Canakinumab within 3 months prior to Baseline (*not applicable for patients rolling-over from CACZ885D2203/ CACZ885D2207M*)
 - d. Rilonacept within 4 weeks prior to Baseline
 - e. Tocilizumab within 6 weeks prior to Baseline
 - f. Etanercept within 2 weeks prior to Baseline
 - g. Infliximab within 4 weeks prior to Baseline
 - h. Adalimumab within 6 weeks prior to Baseline
 - i. Golimumab within 6 weeks prior to Baseline
 - j. Certolizumab within 6 weeks prior to Baseline
 - k. Abatacept within 7 weeks prior to Baseline
 - l. Tofacitinib within 24 hours prior to Baseline
 - m. Rituximab within 24 weeks prior to the Baseline
 - n. Leflunomide within 8 weeks prior to the Baseline
Documentation of a completion of a full cholestyramine elimination treatment after most recent leflunomide use will be required.
 - o. Thalidomide within 4 weeks prior to Baseline
 - p. Cyclosporine within 4 weeks prior to Baseline
 - q. Intravenous immunoglobulin (i.v. Ig) within 8 weeks prior to Baseline
 - r. 6-Mercaptopurine, azathioprine, cyclophosphamide, or chlorambucil within 12 weeks prior to Baseline
 - s. Intra-articular, peri-articular or intramuscular corticosteroid injections within 4 weeks prior to Baseline
 - t. Any other investigational biologics within 3 half-lives prior to the Baseline visit
 - u. Any other investigational drugs, other than investigational biologic treatment, within 30 days (or 3 months for monoclonal antibodies) or 3 half-lives prior to the Baseline visit, whichever is longer
2. History of hypersensitivity to any of the study drugs or to drugs of similar chemical classes or to any of the excipients.
3. History or current diagnosis of ECG abnormalities indicating significant risk of safety for patients participating in the study such as:

- a. Concomitant clinically significant cardiac arrhythmias, e.g., sustained ventricular tachycardia, and clinically significant second or third degree AV block without a pacemaker

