 - b. Thrombocytopenia as per CTC Grade ≥ 1 : Platelets $< LLN - 75.0 \times 10^9/L$ or below
 - c. Any active or recurrent bacterial, fungal (with exception of onychomycosis) or viral infection
 - d. Presence of Human Immunodeficiency Virus (HIV) infection, Hepatitis B or Hepatitis C infections based on screening lab results
 - e. Clinical evidence or history of multiple sclerosis or other demyelinating diseases, or Felty's syndrome

8. History or evidence of tuberculosis (TB) (active or latent) infection or one of the risk factors TB such as but not limited or exclusive to:
 - a. History of any of the following: residence in a congregate setting (e.g. jail or prison, homeless shelter, or chronic care facility), substance abuse (e.g. injection or non-injection); health-care workers with unprotected exposure to patients who are at high risk of TB or patients with TB disease before the identification and correct airborne precautions of the patient, or
 - b. Close contact (i.e. share the same air space in a household or other enclosed environment for a prolonged period (days or weeks, not minutes or hours)) with a person with active pulmonary TB disease within the last year, or
 - c. Evidence of TB infection (active or latent) determined by positive QuantiFERON (QFT-TB G In-Tube) test or positive Purified Protein Derivative (PPD) test (≥ 5 mm induration) at screening or within 2 months prior to the screening visit, according to the national guidelines. If presence of TB infection (active or latent) is established then treatment for TB as per national guidelines must have been initiated or completed prior to randomization. In the absence of national guidelines, the following has been demonstrated: TB has been treated adequately by antibiotics, cure can be demonstrated and risk factors resulting in TB exposure and contracting have been removed.
9. Administration of any investigational drug or implantation of investigational device, or participation in another trial, within 30 days before screening (*not applicable for patients rolling-over from CACZ885D2203/ CACZ885D2207M*).
10. Live vaccinations within 3 months prior to the start of the trial, during the trial, and up to 3 months following the last dose
11. Donation or loss of blood (amount depending on age and weight, 10-20% or more of volume, within 8 weeks prior to first dosing, or longer if required by local regulation

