5.5.8 Prohibited Treatment

Use of the treatments displayed in [Table 5-1](#) is NOT allowed after Screening.

Table 5-1 Prohibited treatment

Medication	Action to be taken
Corticosteroid maintenance (prednisone equivalent > 0.2 mg/ kg/ day or greater than the maximum of 15 mg/ day for children over 60 kg).	Investigational treatment does not need to be discontinued as a result of this protocol deviation (PD)
Anakinra	Investigational treatment to be discontinued ²
Rilonacept, tocilizumab, rituximab and any other biologics ¹ (investigational or marketed)	Investigational treatment to be discontinued ²
Etanercept, adalimumab, infliximab, or any TNF inhibitor (investigational or marketed)	Investigational treatment to be discontinued ²
Leflunomide, thalidomide, cyclosporine, or i.v. Ig	Investigational treatment to be discontinued ²
Tofacitinib	Investigational treatment to be discontinued ²
6-Mercaptopurine, azathioprine, cyclophosphamide, or chlorambucil	Investigational treatment to be discontinued ²
Intra-articular, peri-articular or intramuscular corticosteroid injections	Investigational treatment to be discontinued ²
Any other investigational non-biological drug	Investigational treatment to be discontinued ²
Any live vaccination ¹	Investigational treatment to be discontinued ²
Treatment for tuberculosis	Investigational treatment to be discontinued

¹ It is recommended not to initiate any live vaccination or biologic treatment until 3 months after the last dose of investigational treatment. Killed or inactivated vaccines may be permitted according to the investigator's discretion.

² Investigational treatments must be permanently discontinued but patient will remain in the study and will be followed-up for safety.

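### Two TB rules contradict each other: the PPD cut-off (≥5 mm in exclusion 8c, >5 mm in 6.2.1.2), and ongoing TB treatment (accepted at entry by 8c, a mandatory stop under Table 5-1)

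*Protocol*

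**What the plan says.** Protocol section 4.2 opens with the general rule: "Patients fulfilling any of the following criteria are not eligible for inclusion in this study". Criterion 8c then names evidence of active or latent infection "determined by positive QuantiFERON (QFT-TB G In-Tube) test or positive Purified Protein Derivative (PPD) test (≥ 5 mm induration) at screening" or in the two months before it, with reference to national guidelines. It continues: "If presence of TB infection (active or latent) is established then treatment for TB as per national guidelines must have been initiated or completed", the deadline being randomization. Where no national guidelines exist, it asks for adequate antibiotic treatment, demonstrated cure and removal of the exposure risk.

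Section 6.2.1.2 sets its own cut-off: "A PPD skin induration >5 mm is interpreted as positive result". It then says: "A chest x-ray or QFT-GIT assay is however required to further investigate the nature of the positive PPD skin test". On the outcome it states: "In case of a negative confirmatory test, the patient is eligible for participation/ continuation in the study and no further clinical investigations are needed". It repeats the rule: "Patients with a positive PPD skin test result may be eligible for participation/ continuation only if they have a negative chest x-ray", with a negative QFT-GIT serving equally well. Appendix 4 places indurations of 5 to 9 mm in the low TB-risk group.

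On TB treatment, section 5.5.8 says that use of anything listed in Table 5-1 "is NOT allowed after Screening". The table lists treatment for tuberculosis, with discontinuation of investigational treatment as the action. Section 5.5.9 makes use of a Table 5-1 treatment a mandatory reason to discontinue. The synopsis lists the need for antibiotics against latent TB among its exclusions.

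**The concern.** TB is both a named exclusion and a named reason to stop study drug in a trial of an immunomodulatory agent, run at more than 20 centers with the TB test chosen by local guidelines. Entry and stopping rules of this kind should give one answer for one patient.

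They fail to do so in two places. A PPD of exactly 5 mm falls on different sides of the line in the two sections that define a positive test. And a patient who has started TB treatment without finishing it satisfies 8c but, once randomized, meets a rule that requires study drug to be stopped. The stake is consistent and safe handling of individual patients.

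**Working it through.** No arithmetic applies; the check is to set the rules side by side and run cases through them.

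**PPD cut-off.** Take an untreated patient with no other TB finding.

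| PPD induration | Exclusion 8c | Section 6.2.1.2 | Result |
|---|---|---|---|
| Below 5 mm | Negative | Negative | Agree |
| Exactly 5 mm | Positive, evidence of infection | Negative, no x-ray or QFT-GIT required | Contradict |
| Above 5 mm | Positive, evidence of infection | Positive, x-ray or QFT-GIT required, eligible if negative | Reconcilable, but not cross-referenced |

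The middle row cannot be read away. Even if 6.2.1.2 is taken as the work-up that decides whether infection is established for 8c, that work-up is required only after a PPD that 6.2.1.2 itself calls positive. A 5 mm patient has evidence of infection under 8c, yet no required route to the test that could clear it. Appendix 4 starts its low-risk band at 5 mm, which fits the 8c cut-off.

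**TB treatment.** Take a patient with established infection, at a site that follows national guidelines.

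| TB treatment at randomization | Exclusion 8c | Table 5-1 and 5.5.9 | Synopsis | Result |
|---|---|---|---|---|
| Completed | May enter | Not triggered | Antibiotics no longer required | Agree |
| Started, not completed | May enter | Study drug must be discontinued | Excluded if the antibiotics are for latent TB | Contradict |
| Not started | May not enter | Not reached | Excluded if antibiotics are required for latent TB | Agree |

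Because 8c names started and completed treatment as alternatives, a patient who qualifies only on the first is by definition still to finish the course. Table 5-1 has no exemption for treatment begun before randomization. The table can carry an exception: its corticosteroid row says study drug need not be stopped. The TB row says the opposite. This conflict does not depend on the PPD, since 8c also covers infection found by a positive QFT.

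**The case against.** The best defense is that the protocol is workable as it stands. Section 6.2.1.2 says outright that a PPD-positive patient with a negative confirmatory test is eligible, and the treatment duty in 8c applies only once infection is established. The natural sequence is that 8c screens, 6.2.1.2 works up, and 8c requires treatment if infection is found. This stands. A reader might infer that sites will reach opposite decisions on every PPD-positive patient with a clear x-ray or QFT-GIT. The documents do not support that; what is missing there is a cross-reference.

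On the 5 mm case, section 5.3 has the investigator confirm every criterion before randomization, so the 8c cut-off should be applied at entry. Nothing forbids a work-up at 5 mm, and section 6.2.1 allows a combination of tests. This narrows the problem but leaves two different numbers for one test. Applying 8c alone excludes the 5 mm patient without the confirmatory step that a patient with a larger reaction must be given.

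On TB treatment, Table 5-1 may have been meant for treatment newly started on study, and the synopsis is an abbreviated list. That may be the intent, but neither the table nor 5.5.9 says so.

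A reader might also see a gap on study, because 5.5.9 stops study drug for a confirmed TB diagnosis without defining confirmed. Section 6.2.1.2 expressly covers continuation as well as entry, and its confirmatory test gives the word a natural meaning. No contradictory pair of instructions is shown there.

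**Conclusion.** Two contradictions hold on the text: the cut-off at exactly 5 mm, and the acceptance at entry of unfinished TB treatment that Table 5-1 and 5.5.9 then treat as a reason to stop. The link between 8c and 6.2.1.2 for larger PPD reactions is a lesser matter of cross-referencing.

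The size cannot be calculated. The documents give no frequency for PPD use, PPD positivity or TB treatment at entry. PPD testing is done only where local regulations require it, and the cut-off issue touches a single reading, so the number of patients is probably small. No efficacy endpoint, analysis set or error rate is affected. The second contradiction is assessed for sites with national guidelines; where there are none, 8c already asks for demonstrated cure. The point is worth correcting because it concerns safety rules and the remedy is cheap.

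**What to change.** 1. Use ≥5 mm in both 8c and 6.2.1.2, in line with the 5 to 9 mm band in Appendix 4.
2. Add to 8c a reference to 6.2.1.2, stating that an untreated PPD-positive patient with a negative confirmatory test does not have established infection. Leave a positive QFT to 8c as written. A blanket exclusion for it would contradict the route that 8c gives to treated patients.
3. Make the treatment rules agree in one of two ways. Either require completed TB treatment in 8c by removing the started-treatment alternative, which also brings it closer to the rule 8c applies without national guidelines. Or exempt TB treatment begun before randomization in Table 5-1 and the synopsis; section 5.5.9 refers to the table and would follow.

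The cost is a written amendment. No new type of test is needed, but a patient at exactly 5 mm would now get the x-ray or QFT-GIT already required above 5 mm. Removing started treatment from 8c changes who may enter and may add a few screen failures. The exemption keeps those patients but means giving study drug during TB treatment, which is a medical decision for the sponsor.
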